7.7 Prior and Concomitant Therapy

The inclusion and exclusion criteria ([Section 5.1](#) and [Section 5.2](#), respectively) provide details on prohibited medications and the permitted duration since their last use prior to Screening and/or study drug administration. All medications taken within 90 days before Visit 2/Baseline (randomization) are to be recorded in the CRF/eCRF. Eligible patients will undergo up to a 21-day washout period (no drug onboard) for withdrawal of all medications used for anti-spasticity and/or muscle relaxation prior to randomization (see Inclusion Criterion 6). Subjects will be ineligible for randomization if they concomitantly use any of the medications listed in Appendix 6 (see Exclusion Criterion 5). Table 3 presents the half-life, taper period, and washout period for specific anti-spasticity and/or muscle relaxation medications. Tapering of an existing anti-spasticity drug depends on the dose of the drug and other conditions. The investigator should use medical judgment to safely taper the dose. Under most conditions, the taper should take no more than 2 weeks. For anti-spasticity medications not shown in Table 3, please contact the medical monitor for discussions of the washout period.

Table 3: Taper and Washout Periods for Specific Anti-spasticity and/or Muscle Relaxation Medications, Study OS440-3004

Drug	Half-Life (hours)	Taper Period	Washout Period
Baclofen	3 to 5	3 to 14 days	1 day
Clonidine	12 to 16	3 to 14 days	3 days
Dantrolene	8 to 9	3 to 14 days	2 days
Gabapentin	5 to 7	3 to 14 days	2 days
Zanaflex	3	3 to 14 days	1 day
Diazepam	100	3 to 14 days	3 weeks

All conventional medications regularly used for the treatment of MS, other than anti-spasticity medications, and non-pharmacological therapies (intended to alleviate spasticity, eg, physiotherapy) are allowed provided they have been taken/administered for at least 1 month prior to enrollment and no dose adjustments are expected for the duration of this study.

Changes in either the dose or frequency of concomitant medications taken for the treatment of MS should not be made for the duration of this study. In the event a dose adjustment is needed for a concomitant medication, the Investigator will contact the Sponsor to determine if the subject may remain in the study or needs to be withdrawn.

Ancillary therapy for spasticity such as hydrotherapy, massage, and acupuncture are allowed however, the administration and frequency must be consistent for at least 3 months prior to Screening and throughout the duration of participation in the study. Any deviation from this ancillary therapy is grounds for subject withdrawal.

If a subject is receiving disease-modifying medications (especially interferons, see Inclusion Criterion 5), study visits should be scheduled prior to administration and, if possible, at a consistent time point during the study from when these drugs are administered in order to avoid interference with the temporary increase in spasticity that these medications may produce.

Subjects who experience an acute MS exacerbation/relapse (symptoms including but not limited to visual disturbance, dizziness, tingling, or extreme fatigue lasting greater than 24 hours and occurring at least 30 days after a previous relapse) requiring immediate therapy or adjustment in disease-modifying medication dose (eg, oral or intravenous high-dose steroid therapy), will be discontinued from this study.

Other medication that is considered necessary for the subject's safety and well-being may be given at the discretion of the Investigator. The administration of all medication (including investigational products) will be recorded in the appropriate sections of the CRF/eCRF. If there is any question, the Medical Monitor must be contacted.

Data collection for concomitant medications will include indication, dose, route, dosing frequency, start date, stop date, and will continue throughout the study.

The Investigator or study staff will ask the subject at every study visit whether they have taken any new medications or had changes in their current medications/therapies since the last study visit. It is the responsibility of the Investigator to ensure that any change in concomitant medications/therapies during the study is recorded in the source documentation and entered in the CRF/eCRF.

7.8 Use of Contraception and Pregnancy Testing

Prior to study enrollment, females of childbearing potential and female partners of male subjects must be advised of the importance of avoiding pregnancy during study participation and the potential risk factors for an unintentional pregnancy. Females of childbearing potential include any female who has experienced menarche and who has not undergone successful surgical sterilization (hysterectomy, bilateral tubal ligation/occlusion, or bilateral oophorectomy) or is not postmenopausal (defined as amenorrhea >12 consecutive months). Premenopausal women of childbearing potential must have a negative serum pregnancy test within 21 days before Visit 2 (Baseline) and, if they are sexually active or become sexually active during the study, must use an effective method of birth control such as those listed below during the course of the study. Urine pregnancy testing will be done at Visits 2 through 6.

The following is not an all-inclusive list; the subject must discuss with the Investigator the most appropriate form of birth control:

- Hormonal methods
 - Oral contraceptives
 - Implant
 - Injection
 - Transdermal patch
 - Intravaginal ring
- Intrauterine device (hormonal or non-hormonal)
- Barrier methods
 - Condom (male or female) with spermicide
 - Diaphragm with spermicide
- Complete abstinence

7.9 Treatment Compliance

Subject compliance will be based on drug accountability information. Non-compliance will be defined as subjects taking less than 80% or more than 120% of prescribed study medication as

assessed by the amount of study drug returned by the subject. Dose interruption for more than 5 consecutive days during the titration or maintenance periods will require early study withdrawal of the subject.

8 EFFICACY ASSESSMENTS

8.1 Total Numeric-Transformed Modified Ashworth Scale

The TNmAS is considered the primary clinical measure of muscle spasticity in subjects with neurological conditions. It is a useful 6-point rating scale to measure abnormality in tone or the resistance to passive movements, since there is no clinically direct method for measuring spasticity.

When initially developed in the early 1960s ([Ashworth 1964](#)) to estimate the efficacy of anti-spastic drugs in subjects with MS, it was a 5-point scale, with a grade score of 0 to 4. In 1987, the grade “1+” was added and slight changes were proposed on the definitions of each score in order to increase the sensitivity of the measure and facilitate scoring. The new measure was then called the Modified Ashworth Scale (mAS) and it is considered the gold standard for measuring spasticity ([Bohannon and Smith 1987](#)).

Although there are no standardized guidelines for its use, it can be applied to muscles of both the upper or lower body. The rater should extend the client’s limb from a position of maximal flexion to maximal extension until the first soft resistance is felt. Moving a subject’s limb through its full range of motion should be done within 1 second by counting “one thousand and one.”

It is suggested that the testing of the upper limbs should take place while the subject is lying supine, with the upper limbs parallel to the trunk, elbows extended, wrists in a neutral position, and the lower limbs positioned parallel to one another. Exceptions are made for the shoulder extensors, where the arm should be moved from extension to 90 degrees of flexion, and for the shoulder internal rotators, where the arm should be moved from neutral to a maximum external rotation. For the lower limbs, it is recommended that the subject be lying on their side. Specifically for testing the soleus muscle, the hips and knees should be positioned in 45 degrees of flexion and the ankle is moved from maximum plantar flexion to maximum dorsiflexion. For the gastrocnemius muscle, hips should be in 45 degrees of flexion with the knees in maximum extension and the ankle is moved from maximum plantar flexion to maximum dorsiflexion. For the quadriceps femoris muscle, knees and hips should be in maximal extension and the knee is moved from maximum extension to maximum flexion. Throughout testing, the subject should be instructed to remain calm and relaxed, and when repeated testing is undertaken, testing should be initiated at the same time of the day to minimize possible changes in spasticity levels due to medication interaction.

To arrive at the TNmAS-MAL score, the total numerical score of a limb accounts for the sum of the 3 main joint muscular group scores. If two or more limbs tie for “Most Affected” at Visit 2 (Baseline), then the Visit 5 (Day 84) scores for the tied limbs will be assessed and the one with the worst score at Visit 5 will become the MAL in the primary analysis. In the case of a tie at Visit 2 (Baseline) and at Visit 5, then all of the scores from Visit 2 to Visit 5 will be summed and

the highest (worst) total will be flagged as the MAL. If a subject discontinues early, then the early termination visit scores will be used in place of the Visit 5 scores.

The TNmAS-MAL assessment will always be performed by the study evaluator (someone other than the investigator) who has been appropriately trained to perform and assess the TNmAS-MAL, and when possible all TNmAS-MAL assessments should be performed for a particular subject by the same study evaluator throughout the study prior to any scheduled lab draw. The most affected limb will be determined by the study evaluator and the subject. The study evaluator must remain blinded to the subject's overall clinical, safety, and CGIC assessments.

The TNmAS-MAL assessment will be done at the visits specified in Table 1. The mAS and TNmAS-MAL are provided in Appendix 1.

8.2 Clinical Global Impression of Change

The CGIC was developed for use in National Institute of Mental Health (NIMH)-sponsored clinical trials to provide a brief, stand-alone assessment of the clinician's view of the subject's global functioning prior to and after initiating a study medication (Guy 1976). The CGIC scale will be used to measure the overall change in the subject's condition since starting the study.

In clinical research, the CGIC is administered by an experienced clinician who is familiar with the disease under study and the likely progression of treatment. Consequently, the CGIC rater can make an expert clinical global judgment about the severity of the illness across various time points within the context of that clinical experience. The clinician makes a judgment about the total picture of the subject at each visit: the illness severity, the subject's level of distress and other aspects of impairment, and the impact of the illness on functioning. The CGIC is rated without regard to the clinician's belief that any clinical changes are or are not due to medication and without consideration of the etiology of the symptoms.

The investigator will evaluate the subject's status on a -3 to +3 scale judging whether there had been a change from significant worsening to significant improvement relative to Visit 2 (Baseline) and must have access to the TNmAS. The CGIC scale is provided in Appendix 3.

8.3 Patient Global Impression of Change

The PGIC is a standard instrument that is a well validated outcome measure. The 7-point PGIC measures change in the subject's overall status using the following categorical scale:

- 1 = Very much improved
- 2 = Much improved
- 3 = Improved
- 4 = No change
- 5 = Minimally worse

- 6 = Much worse
- 7 = Very much worse

The PGIC will be done at the visits specified in Table 1. The PGIC is provided in Appendix 4.

8.4 Expanded Disability Status Scale

The EDSS is a method of quantifying disability in MS and monitoring changes in the level of disability over time. It is widely used in clinical trials and in the assessment of people with MS. The scale was developed by John Kurtzke in 1983 as an advance from his previous 10-step Disability Status Scale (DSS) (Kurtzke 1983). The EDSS scale ranges from 0 to 10 in 0.5-unit increments that represent higher levels of disability. Scoring is based on an examination by a neurologist.

EDSS steps 1.0 to 4.5 refer to people with MS who are able to walk without any aid and is based on measures of impairment in eight functional systems (FS): pyramidal (weakness or difficulty moving limbs), cerebellar (ataxia, loss of coordination, or tremor), brainstem (problems with speech, swallowing, and nystagmus), sensory (numbness or loss of sensations), bowel and bladder function, visual function, cerebral (or mental) functions, and other. Each FS is scored on a scale of 0 (no disability) to 5 or 6 (more severe disability). EDSS steps 5.0 to 9.5 are defined by the impairment to walking.

The EDSS assessment will be done at the visits specified in Table 1. The EDSS is provided in Appendix 2.

9 SAFETY ASSESSMENTS

Safety will be assessed by the monitoring of TEAEs volunteered, observed, and elicited by general questioning in a non-suggestive manner. Changes in vital signs, clinical laboratory test results, 12-lead electrocardiograms (ECGs), the USP questionnaire, and the C-SSRS will also be assessed.

9.1 Medical/Surgical History

A complete medical and surgical history will be obtained at Visit 1 (Screening), which will record previous respiratory, cardiovascular, gastrointestinal, hepatic, nephro-urologic, metabolic, allergic, infectious, gynecologic, musculoskeletal, endocrine, neurologic, psychiatric, dermatologic, allergic, hematologic, and any other diseases.

9.2 Vital Signs

Heart rate and BP will be measured at all visits. Blood pressure measurements will be made using a sphygmomanometer with an appropriate cuff size for the individual subject.

To evaluate the potential of arbaclofen to trigger orthostatic hypotension, BP and heart rate will be measured twice at each study visit. Orthostatic testing should take place in a quiet room, preferably at a temperature between 20°C and 24°C (68°F to 75°F). Emptying the bladder

before testing is also recommended. The diagnosis of orthostatic hypotension is established by measuring the BP in the supine and then in the standing position, at least 3 minutes apart, and noting a substantial drop accompanied by symptoms of dizziness or syncope. A positive response is considered if systolic BP falls below 20 mmHg and diastolic BP 10 mmHg of baseline. If symptoms occur, the subject should be returned to the supine position immediately.

Vital signs, including BP, heart rate, respiratory rate, and body temperature, will be measured after the subject has been in a supine position quietly for 10 minutes. Then, with the subject in a standing position, BP and heart rate will be measured again after the supine assessment is completed.

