9.6.2 Urinary Symptom Profile[®] Questionnaire

The USP is a health-related quality of life questionnaire developed in 2005 by the French Association of Urology and validated in 2008 ([Haab et al 2008](#)). It is composed by 13 items in 3 dimensions to assess urinary symptoms among adults (both men and women) with stress, urge, overactive bladder, or urinary obstructive symptoms. It is administered with a time frame over

the past 4 weeks. The USP is a valuable tool for self-administration by the subject to complement clinical measures and diagnosis due to it being a valid and reliable questionnaire providing comprehensive evaluation of all urinary disorders and their severity. It also allows the pathology screening and contributes to the differential diagnosis of these symptoms. Due to the potential risk of arbaclofen to produce urinary problems, mainly at bladder level (as seen in some animal toxicological studies; see the current arbaclofen Investigator's Brochure [IB]), the utilization of this questionnaire has been implemented in the context of this study to monitor urinary symptomatology and rule out any complication that could be developed during the course of the study. An increase of 4 points in the total USP score from the previous visit will be considered an AE.

The USP questionnaire will be completed by the subject at the visits specified in Table 1. The USP is provided in Appendix 7.

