USP® questionnaire	X	X	X	X	X	X
Adverse event assessment		X	X	X	X	X
Concomitant medications/therapies	X	X	X	X	X	X

C-SSRS = Columbia–Suicide Severity Rating Scale; TNmAS-MAL = Total Numeric-transformed modified Ashworth Scale score of the most affected limb; EDSS = Expanded Disability Status Scale; CGIC = Clinical Global Impression of Change; PGIC = Patient Global Impression of Change; USP = Urinary Symptom Profile.

Table 1 - Footnotes:

1. Vital signs will be measured with the subject in a supine position and in a standing position 3 minute after the supine assessment is completed. Body temperature and respiratory rate will be measured only during the supine assessment.
2. Premenopausal women of childbearing potential must have a negative serum pregnancy test within 28 days before Visit 2 (Baseline). Urine pregnancy testing will be done at Visits 2 through 6.
3. The TNmAS-MAL assessment will be performed prior any scheduled lab draws and will always be done by the study evaluator (someone other than the investigator) who has been appropriately trained to perform and assess the TNmAS-MAL, and when possible all TNmAS-MAL assessments should be performed for a particular subject by the same study evaluator throughout the study. The most affected limb will be determined by the study evaluator.
4. Performed by the investigator or sub-investigator not functioning as the study evaluator for the particular subject.

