7.3.3. Handling of Early Termination Visit Information

If a subject is terminated early from this study the early termination visit data will be analyzed at the closest scheduled visit. If the closest visit has valid data, the early termination data will be assigned to the next available visit.

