7.4. Planned Study Analyses

7.4.1. Statistical Summaries: Descriptive and Inferential

All statistical tests will be two-sided and a difference resulting in a p-value of less than or equal to 0.05 will be considered statistically significant. All p-values will be rounded to and displayed in four decimals. If a p-value less than 0.0001 occurs it will be shown in tables as <0.0001.

Descriptive summaries of variables will be provided where appropriate. For continuous variables, the number of non-missing values (n) and the median, mean, standard deviation, minimum, and maximum will be tabulated by treatment. For categorical variables, the counts and proportions of each value will be tabulated by treatment. Expansion of descriptive table categories within each treatment may occur if such elaborations are thought to be useful.

For the summary statistics of all numerical variables unless otherwise specified, minimum and maximum will be displayed to the same level of precision as reported. Mean and median will be displayed to one level of precision greater than the data collected. The standard deviation / standard error will be displayed to two levels of precision greater than the data collected.

Change from baseline scores will be calculated as the post-baseline measurement minus the baseline value.

All collected data will be presented in listings. Data not subject to analysis according to this plan will not appear in any tables or figures but will be included in the data listings.

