10.4. Vital Signs

Vital sign results will be summarized descriptively for each treatment group by time point for the observed value as well as for the change from baseline value. All vital sign data by subject will be presented in a listing. Unscheduled visit results will not be summarized but will be included in subject data listings.

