10.6. Other Safety Measures

C-SSRS results will be presented in subject data listings.

USP summary scores (stress urinary incontinence score, overactive bladder score, and low stream score) will be summarized descriptively for each treatment group by time point for the observed value as well as for the change from baseline value. All USP data (including the 10 individual questions) will be presented in listings.

ECG parameters will be summarized descriptively for each treatment group by time point for the observed value as well as for the change from baseline value. All ECG data will be presented in listings.

No other safety analyses have been prospectively defined. If, however, after study results are reviewed, or the DSMB or Sponsor recommend additional safety parameters or analyses be completed, they will be fully described and documented in the final clinical study report. The SAP does not need to be amended to complete any other safety measures identified as post-hoc.

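### Supine and standing readings are taken to evaluate orthostatic hypotension, but the SAP pre-specifies no within-subject postural change and no by-arm count of positive responses

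*Protocol*

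**What the plan says.** Protocol 9.2 names a drug-specific safety question and the measurements meant to address it: "To evaluate the potential of arbaclofen to trigger orthostatic hypotension, BP and heart rate will be measured twice at each study visit". It describes the diagnosis as a substantial drop from supine to standing, with readings at least 3 minutes apart, together with dizziness or syncope. It then sets a numerical criterion: "A positive response is considered if systolic BP falls below 20 mmHg and diastolic BP 10 mmHg of baseline".

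The SAP knows that both postures are recorded. Footnote 1 to its schedule of assessments (SAP 5.1, Table 1) reads: "Vital signs will be measured with the subject in a supine position and in a standing position 3 minute after the supine assessment".

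The planned analysis is in SAP 10.4: "Vital sign results will be summarized descriptively for each treatment group by time point for the observed value as well as for the change", the change being that since baseline. A by-subject listing is added, and posture is not mentioned. SAP 7.4.1 fixes what change from baseline means: "Change from baseline scores will be calculated as the post-baseline measurement minus the baseline value". Protocol 11.5 likewise promises only descriptive vital-sign summaries by visit and arm, with no safety tests. SAP 10.6 closes the list, "No other safety analyses have been prospectively defined", but lets further safety analyses be added later and documented in the study report without amending the SAP.

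**The concern.** Orthostatic hypotension is a change between two postures in one person on one occasion. The SAP's only change variable runs between visits. It can show whether standing pressure at Day 84 differs from standing pressure at Visit 2, but not whether a subject's pressure falls on standing up. The protocol's responder criterion appears nowhere in the SAP.

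What is at stake is a by-arm answer, defined in advance, to a safety question that the protocol itself poses. Without it, the threshold, the visits that count and the denominator would all be chosen after the data are unblinded. Efficacy inference is not touched.

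**Working it through.** The plan gives no figure to reproduce here, so the check has three parts.

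**1. Trace each possible source of a postural result.**

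| Planned output | Standing minus supine within subject? | Count meeting 20/10 mmHg by arm? |
|---|---|---|
| SAP 10.4, observed values | No. If tabulated by posture (the SAP does not say), a difference of means at most | No |
| SAP 10.4 with 7.4.1, change from baseline | No, between visits | No |
| SAP 10.4, listing | Raw values only | No |
| SAP 10.1, adverse events | No | No; symptoms and reported diagnoses only |
| SAP 10.6, other measures | None planned | None planned |

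Even the difference of means needs the same subjects in both postures. Inclusion requires EDSS of at least 3.0 with no upper limit (Protocol 5.1), so some subjects may have no standing reading.

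**2. Ask whether summaries by posture could yield the count.** The inputs are assumptions, because the documents give no blood pressure distribution. They are a mean standing-minus-supine systolic change of -3 mmHg, the same SD in each posture, a correlation r between the two readings, and normality.

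- SD of the postural change = SD × √(2(1 − r))
- Share falling at least 20 mmHg = Φ((−20 + 3) / SD of change) = Φ(−17 / SD of change)

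With SD = 15 mmHg in each posture and 170 subjects per arm (Protocol 5):

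| r | SD of change (mmHg) | Share falling ≥ 20 mmHg | Of 170 |
|---|---|---|---|
| 0.5 | 15.00 | 12.9% | about 22 |
| 0.7 | 11.62 | 7.2% | about 12 |
| 0.8 | 9.49 | 3.7% | about 6 |
| 0.9 | 6.71 | 0.6% | about 1 |

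The posture-specific means and SDs are the same in every row, so the table that SAP 10.4 could produce would look the same in every row. Over SDs of 12 to 18 mmHg and r of 0.5 to 0.9, the share runs from 0.1% to 17.3%. The count needs each subject's own difference. This illustration uses the systolic limb only; adding the diastolic limb would bring in further unknown correlations.

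**3. Identify which visits bear on the question.** Titration, maintenance and taper last 9 + 75 + 7 = 91 days (Protocol 4.1), so Visit 6 at Day 92 nominally follows the last dose. On-treatment readings come from Visits 3, 4 and 5: at most 510 × 3 = 1,530 pairs, or 170 × 3 = 510 per arm, before dropout and missing standing readings.

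SAP 7.3.3 complicates this: "If a subject is terminated early from this study the early termination visit data will be analyzed at the closest scheduled visit". A subject off drug for more than 5 consecutive days must be withdrawn (Protocol 12.4). A termination reading can therefore be taken off drug and still be assigned to Visit 3, 4 or 5.

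**The case against.** The strongest reply is that the plan is not silent on orthostatic hypotension. The protocol's diagnosis includes symptoms, and dizziness, syncope or orthostatic hypotension reported on treatment would be tabulated by preferred term and arm under SAP 10.1. The pairs are collected and listed. SAP 10.6 permits a later, documented table, and because safety is untested, that table would spend no alpha. Protocol 11.5 never promises an incidence table, so the SAP breaks no analysis commitment.

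Most of this stands, and it limits the point. A reader might infer that the plan cannot answer the orthostatic question at all. The documents do not support that: the symptomatic form has a by-arm output, and the rest can be derived from retained data. What the reply does not supply is a link between symptoms and the measured drop, or a count against the protocol's criterion.

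A reader might also infer that asymptomatic falls are bound to be missed as adverse events, because the protocol sets an explicit rule for urinary symptoms ("An increase of 4 points in the total USP score from the previous visit will be considered an AE") and none for a positive orthostatic response. That goes too far. Protocol 9.7.2.1 defines an adverse event to include any unfavourable sign, so an investigator may record a marked fall. The contrast shows only that recording is left to judgement, which makes the adverse event tables an uncertain substitute.

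The criterion is also loosely worded. Read literally, its baseline could be Visit 2 rather than the same-visit supine reading, and its relation to symptoms is not stated. This is a reason to settle it before unblinding.

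**Conclusion.** The point holds as a gap in pre-specification. The protocol takes paired readings for a stated purpose and gives a responder criterion, while the SAP plans neither the within-subject postural change nor the share of positive responses by arm. This is worth correcting but not critical: no data are lost, symptomatic events are tabulated, a post hoc table is allowed, and efficacy is unaffected.

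The size of any effect in this trial cannot be estimated, because the documents give no expected rate of positive responses. The spread of 0.6% to 12.9% shows only that summaries by posture do not determine the count. It rests on the assumed mean, SD, correlations and normality.

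**What to change.** Amend SAP 10.4 before unblinding, keeping everything descriptive as Protocol 11.5 requires.

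1. Derive standing-minus-supine change in systolic BP, diastolic BP and heart rate within subject and visit. Summarise it by arm and visit.
2. Define a positive response as a same-visit fall from supine to standing of at least 20 mmHg systolic and at least 10 mmHg diastolic. The clinical team should confirm whether both limbs or either one is required, confirm that baseline in Protocol 9.2 means the same-visit supine reading, and state whether symptoms are required. If symptoms are recorded, show positives with and without dizziness or syncope.
3. Report n (%) positive by arm at each visit and at any on-treatment visit (Visits 3 to 5). Show Visit 6 separately and identify subjects already positive at Visit 2.
4. Count an early-termination reading as on treatment only if the subject was still taking study drug.
5. Use subjects with both readings as the denominator, and give the number without a standing reading by arm.

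The cost is a few derived variables, one or two extra descriptive tables and a short clinical decision on the criterion. No new data, no hypothesis test and no protocol amendment are needed.
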